4.3.3 Randomization and Study Groups

Participants will be randomly allocated to either an Immediate Group or a Delayed Group after completing the baseline collection. The Immediate Group will be introduced to the gait modification and sent home with the sensorized shoes to begin the intervention as described below. The Delayed Group will schedule their

[figure not shown]

Figure 1. Sensor module construction and placement within the shoe. IMU, inertial measurement unit (accelerometer and gyroscope).

secondary baseline for 6 weeks in the future and receive no intervention for that time period. After the 6 weeks of no intervention, the Delayed Group participants will return to the lab to receive their secondary baseline assessment and begin the intervention thereafter. We will use a variable block size stratified (KL grade and sex) randomization sequence with allocations sealed in envelopes, kept by [name], and revealed after the baseline data collection is complete.

4.3.4 Data Collection

An identical baseline, secondary baseline, follow-up, and retention gait assessment (Table 1) will be conducted at the Motion Analysis and Biofeedback Laboratory in UBC Hospital. In a delayed-control study design the Delayed Group undergoes both a control condition and an intervention condition. For the Delayed Group, the control condition is assessed as the change from the baseline to the secondary baseline assessments, while the intervention is assessed as the change from the secondary baseline to the follow-up assessments. The Immediate group does not need the secondary baseline as they will only be undergoing the intervention condition, which is assessed as the change from the baseline to the follow-up assessment.

These assessments will consist of questionnaires, a timed stair climb, and over-ground gait analysis. These sessions will be conducted by [name] and [name]. These assessments will last 1.5 hours each.

Table 1. Timepoints for each data collection broken down by group. Each of the data collection appointments consists of questionnaires, a timed stair climb, and the gait analysis as described below.

	Week 0	Week 6	Week 10	Week 12	Week 16
Delayed Group	Baseline	Secondary Baseline		Follow up	Retention
Immediate Group	Baseline	Follow up	Retention		

4.3.4 A) Questionnaires & the Timed Stair Climb:

Baseline & Secondary Baseline Questionnaires:

Q1: 11-point numerical rating scale (NRS) depicting average knee pain over the previous week where 0 = “no pain”, 10 = “worst pain imaginable”

Q2: Knee Injury and Osteoarthritis Outcome Score (KOOS) [55]

Q3: Pain Catastrophizing Scale [56]

Q4: Arthritis Self-Efficacy Scale [57]

Q5: Expected global rating of change in pain and physical function using a 15 point Likert scale where -7 = “a very great deal worse” and +7 = “a very great deal better” [58]. This will be administered at the baseline for the Immediate Group and the secondary baseline for the Delayed Group.

Follow-up Questionnaires:

Q1: 11-point numerical rating scale (NRS) depicting average knee pain over the previous week where 0 = “no pain”, 10 = “worst pain imaginable”

Q2: Knee Injury and Osteoarthritis Outcome Score (KOOS) [55]

Q3: Perceived global rating of change in pain and physical function using a 15-point Likert

scale where -7 = “a very great deal worse” and +7 = “a very great deal better” [58].

Q4: Satisfaction with the gait modification program and the telerehabilitation sessions using a 7-point Likert scale where -3 = “extremely unsatisfied” and +3 = “extremely satisfied”.

Q5: Convenience of telerehabilitation sessions on an 11-point NRS where 0 = “extremely inconvenient” and 10 = “extremely convenient”.

Q6: Difficulty of performing the gait modification during daily walking on an 11-point NRS where 0 = no difficulty/easy and 10 = most difficulty imaginable/unable.

Retention Questionnaires:

Q1: 11-point numerical rating scale (NRS) depicting average knee pain over the previous week where 0 = “no pain”, 10 = “worst pain imaginable”

Q2: Knee Injury and Osteoarthritis Outcome Score (KOOS) [55]

Q3: Perceived global rating of change in pain and physical function using a 15-point Likert scale where -7 = “a very great deal worse” and +7 = “a very great deal better” [58].

Q4: Difficulty of performing the gait modification during daily walking on an 11-point NRS where 0 = no difficulty/easy and 10 = most difficulty imaginable/unable.

At the baselines, medical history, anthropometrics (height, body mass etc.), age, and symptom duration will also be recorded by the assessor. At each assessment, a timed stair climb will be conducted as an objective measure of physical function. This will take place in a stairwell adjacent to the laboratory. The time taken to climb 12 steps (1 flight) will be recorded using a hand-held stop watch with the instruction to “climb as quickly, but safely as possible” [59]. Two repetitions of this test will be performed, and the fastest time will be used.

4.3.4 B) Gait Analysis:

A gait assessment will be performed at the baselines and follow up using identical procedures. A total of 54 reflective markers (45 lower limb, 9 upper limb) will be affixed to the skin bilaterally over key anatomical landmarks as is standard in our laboratory [26]. Fourteen high-speed cameras (sample rate = 120 Hz) will track the positions of these markers and two floor-embedded force platforms (sample rate = 1200 Hz) will measure ground reaction forces. Five passes along the 10m instrumented walkway will be performed shod, wearing the sensorized shoes for standardization. Walking speed at the baseline assessment will be measured using two timing gates placed at a known distance along the walkway. At follow-up, participants will first complete five walking passes at a self-selected speed and then be constrained to walk within $\pm 5\%$ of their baseline walking speed, due to the impact of walking speed on joint moments. After walking in the motion capture system, a lap of the hallways around our laboratory space will be performed while wearing the sensorized shoes (approximately 3 minutes total). This will provide a controlled measurement of FPA from the sensorized shoe for comparison with FPA measured during daily at-home walking. After the baseline appointment, the randomization will be revealed, and the participant will either be allocated to the Immediate Group or the Delayed Group. The Immediate Group will undergo the intervention condition (see section 4.3.5). Conversely, the Delayed Group will undergo the control condition first (see section 4.3.6), and then return for a secondary baseline, after which they would enter the intervention condition (see section 4.3.5).

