4.3.6 Control Condition: Wait period

Participants allocated to the Delayed Group at the baseline assessment will be sent home to

undergo a 6-week waiting period. During these 6 weeks they will be asked to maintain their current level of activity. No data will be collected during this time. After the 6-week waiting period, the Delayed Group will return for a secondary baseline (identical to the original baseline). This will constitute the pre-post data collection for the control condition. They will then enter the intervention condition as described above in section 4.3.5.

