1.1 Statistical Analysis

Statistical analyses will be performed by an independent statistician (to be determined). Means and standard deviations across all participants will be calculated for each outcome measure and baseline demographic characteristics. Baseline data will be presented as descriptive data using measures of central tendency. Alpha will be set at 0.05 for all testing.

The primary focus of this study is the feasibility of the intervention. The use of a delayed-control design will be implemented to secondarily assess the efficacy of the intervention. Feasibility outcomes will be reported via summary statistics with a focus on the primary outcomes listed above.

1.1.1 Primary Statistical Testing:

Performance of the modification at the primary end point (6-week follow up) will be examined as outlined in comparison 1 below. All other outcomes measured at baseline, follow up and retention will also be examined using the comparisons below but are considered secondary to the feasibility and performance outcomes.

The statistical comparisons for laboratory-measured outcomes in descending order of priority:

- 1) Between group change at week 6 and week 10 (Delayed Group Secondary Baseline vs Immediate Group Follow up) assessed using an analysis of covariance for the difference in follow-up values while adjusting for baseline values.
- 2) Within-subject comparison of the Delayed Group intervention period, using the Delayed Group as their own control (Delayed Group Follow up vs Delayed Group Secondary Baseline) assessed using a mixed effects model with the participant as the random effect to account for the within-subject nature of the data.
- 3) Within-subject comparison of both groups' data from the intervention (excluding the Delayed Group control period) assessed using a repeated measures analysis of variance across baseline, follow up, and retention timepoints.

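### Speed-constrained walking is described only at follow-up, so the week-6 joint-moment comparison may be speed-controlled in one arm only

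*Protocol*

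**What the plan says.** Protocol section 4.3.4 B describes walking speed visit by visit. For baseline: "Walking speed at the baseline assessment will be measured using two timing gates placed at a known distance along the walkway". For follow-up: "At follow-up, participants will first complete five walking passes at a self-selected speed and then be constrained to walk within" a band of ±5% around the speed recorded at baseline. The reason given is that speed influences joint moments. That paragraph gives no speed rule for the secondary baseline or for retention.

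Section 4.3.6 describes the Delayed Group's visit after the waiting period: "the Delayed Group will return for a secondary baseline (identical to the original baseline". Table 1 places that visit at week 6, alongside the Immediate Group's follow-up.

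Two general sentences point the other way. Section 4.3.4 opens with "An identical baseline, secondary baseline, follow-up, and retention gait assessment (Table 1) will be conducted", and 4.3.4 B opens with "A gait assessment will be performed at the baselines and follow up using identical procedures".

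The first comparison in SAP section 1.1.1 is "Between group change at week 6 and week 10 (Delayed Group Secondary Baseline vs Immediate Group Follow up", analysed by ANCOVA with adjustment for baseline values. H5 in the protocol makes the same week-6 contrast for the knee adduction moment (KAM) late-stance peak and impulse, and expects no significant increase in the knee flexion moment. Section 4.4.2 lists joint moments as secondary outcomes, with KAM impulse leading that family.

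**The concern.** The protocol names walking speed as an influence on joint moments and introduces a procedure to hold it. Read literally, that procedure runs in only one of the two arms at the time point where the arms are compared. A change in the Delayed Group's comfortable speed over six weeks would then enter the KAM and knee flexion contrasts alongside any effect of the gait modification, and the plan could not separate the two.

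It also matters for data capture. If staff follow the text as written, no speed-matched passes will exist for the Delayed Group at week 6, and they cannot be recovered afterwards.

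**Working it through.** **Step 1: what each visit provides, read literally.**

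| Visit | Week | Self-selected passes | Passes within ±5% of baseline speed |
|---|---|---|---|
| Baseline, both groups | 0 | yes, speed timed | not applicable |
| Immediate follow-up | 6 | yes | yes |
| Delayed secondary baseline | 6 | yes (copy of baseline) | none described |
| Delayed follow-up | 12 | yes | yes, but which baseline is the reference is not stated |
| Retention | 10 or 16 | not specified by speed | not specified by speed |

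The assessments cannot all be literally identical, because follow-up has a second set of passes that the first baseline cannot have. Section 4.3.6 ties the secondary baseline to the original baseline, not to follow-up.

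**Step 2: which data can feed comparison 1 at week 6.**

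- Constrained Immediate passes against Delayed passes: speed is held on one side only.
- Self-selected passes in both groups: like for like, but speed is not held on either side.
- Constrained passes in both groups: the option that fits the protocol's rationale, but the Delayed passes are not described.

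Neither document says which follow-up passes supply the joint moments.

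**Step 3: whether the ANCOVA repairs it.** Let e be the percentage change in a joint moment per 1% change in speed, and let s_I and s_D be the mean percentage changes in speed from week 0 to week 6 in the passes analysed. To first order:

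estimated difference (Immediate minus Delayed) = intervention effect + e × (s_I − s_D)

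The baseline moment carries no information on a speed change that happens later, so adjusting for it does not remove the second term. Neither document adds walking speed as a covariate. With constrained Immediate passes, s_I is kept within ±5%, while s_D has no limit. If s_D averages zero, and s_I is also near zero, the second term vanishes. Individual speed changes then only add variance in the Delayed arm.

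**Step 4: scale.** The plan gives no speed-to-KAM relation, so there is no figure of its own to reproduce. The values of e and s_D below are assumptions. Setting s_I = 0, the absolute distortion is |e| × |s_D|:

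| Assumed absolute elasticity | 1% drift | 3% drift | 5% drift | Drift that equals 2% |
|---|---|---|---|---|
| 0.25 | 0.25% | 0.75% | 1.25% | 2 / 0.25 = 8% |
| 0.5 | 0.5% | 1.5% | 2.5% | 2 / 0.5 = 4% |
| 1.0 | 1.0% | 3.0% | 5.0% | 2 / 1.0 = 2% |

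The 2% benchmark comes from protocol section 4.3.1 B, which uses it as the screening cut-off for KAM impulse and reports it as the average KAM reduction at about 10° of toe-out.

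**Step 5: what matching would remove.** Drifts of 2% and 4% fit inside the ±5% band, so they could persist after matching; a drift of 8% could not. The table therefore shows sensitivity to speed and is not the gain from the fix. The fix puts the same limit on both arms and removes departures beyond 5% in the Delayed Group.

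**The case against.** The strongest reply is that the two general sentences show an intention to use one procedure at every visit; the second even refers to the baselines in the plural. That is a fair reading of intent. It leaves the text in conflict with itself, however, and the only sentence that describes constrained passes limits them to follow-up. The passages need reconciling either way.

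A second reply is that self-selected passes are planned at both week-6 visits, so a like-for-like comparison is already available. This stands. A reader might infer that the week-6 analysis definitely sets constrained gait against unconstrained gait; the documents do not say so. The stated reason for the constraint makes that choice likely, and falling back on self-selected passes gives up the control that the protocol says is needed.

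Third, nothing in the documents points to a systematic drift. The Delayed Group receives no intervention and is asked to keep its activity level. This also stands, as does uncertainty about the sign: KAM impulse is an area under a moment-time curve, so moment size and stance duration both contribute.

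Fourth, a reader might infer that SAP comparison 2 (Delayed follow-up against secondary baseline) has the same mismatch. That depends on an undefined term. If the baseline speed used at week 12 is the one measured at the secondary baseline, follow-up is matched to exactly the visit it is compared with. A mismatch arises only if the reference is the week-0 speed.

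**Conclusion.** The point holds as a conditional one. As written, the protocol describes speed-constrained passes for the Immediate Group at week 6 and none for the Delayed Group. If the constrained passes supply the joint moments, as the rationale implies, the between-group contrasts for KAM and knee flexion moments are speed-controlled in one arm only, and baseline adjustment does not correct this.

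Size and direction are unknown. The scenarios in the working range from 0.25% to 5% and rest wholly on assumed elasticities of 0.25 to 1.0 and assumed mean drifts of 1% to 5%. They show that a drift of a few percent could rival the protocol's 2% benchmark; they do not show that it will. With no mean drift there is no bias, only added variance.

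A reader might also infer a threat to the trial's main result, because comparison 1 heads the SAP list. The documents do not support that. The SAP gives comparison 1 its primary role for performance of the modification, and the speed rule is justified by joint moments alone. The effect shown is confined to the secondary joint-moment outcomes.

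**What to change.** - In protocol section 4.3.4 B, use the same two sets at the secondary baseline and at retention as at follow-up: five self-selected passes, then passes within ±5% of a named reference speed. Bring section 4.3.6 and the two general sentences on identical assessments into line with this.
- Name the reference speed: the week-0 speed for comparison 1, with the reference for the Delayed Group's week-12 and week-16 visits stated explicitly. The latter settles whether comparison 2 is matched.
- In SAP section 1.1.1, pre-specify that joint-moment comparisons use the speed-matched passes, with the self-selected passes as a sensitivity analysis.

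The cost is a wording change in both documents and about five extra walking passes at each visit concerned. These visits are already scheduled and the timing gates are already in use, so no new visit or equipment is needed. The sample size does not change.

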4.3.5 Intervention Condition: Gait modification

The intervention will be delivered via telecommunication technology, except for an introduction

to gait modification at the baseline appointment. Five telerehabilitation sessions will be conducted over the six weeks between baseline and follow-up appointments. These sessions will be conducted via a password protected official UBC Zoom videoconference application (Zoom Video Communication, Inc., USA) when possible, and a telephone when not. The study trainer will provide a meeting link and password ahead of the scheduled appointment via email. A review of the participants' practice, perceived confidence in performing the gait modification, difficulty in performing the gait modification, daily pain levels over the day and during walking, and adverse events will be recorded by the study trainer. If possible, the participant will "demonstrate" their gait modification on video. No audio or video recordings will be kept, only notes taken by the study trainer during the session. The sessions will last between 15 and 30 minutes. Outside of these sessions, participants will be expected to practice their gait modification in as much of their walking activity as possible. Practice performance will be monitored by the sensorized shoe.

The direction of the gait modification (toe-out or toe-in) will be dictated by the gait screen (section 4.3.1-A), while the magnitude of the increase to FPA will be self-selected, with the goal of increasing "as much as is comfortable". At baseline, the participant will be shown what their natural FPA looks like and what an increase FPA might look like, while being encouraged to use that as a reference when they are unsure if they have increased enough. The telerehabilitation appointments will serve to guide the participants in performing their modification. To assist participants with adherence and self-efficacy we will use, behaviour change techniques derived from physical activity and exercise interventions for knee OA during the telerehabilitation appointments [60]. These will include: 1) a discussion of the benefits related to performing the gait modification in their daily walking, 2) co-development of realistic goals for practicing the gait modification, 3) identification of potential barriers to practice and possible solutions, and 4) encouragement to self-monitor and use the diary to track progress. These techniques will be revisited at each telerehabilitation session with the study trainer to promote accountability, review successes and failures, and collaborate on adjusting goals or finding solutions to barriers.

At-home walking between the baseline and follow-up data collection appointments will be monitored using the sensorized shoes. Participants will be asked to wear the shoes during as much of their daily outdoor walking activity as possible but to record at least 10 minutes per day (or 70 minutes per week). The sensor will be turned "on" immediately before beginning, and "off" immediately after completing a walk. One hour of charging will be needed every 2-3 days to maintain battery power. Apart from these two actions, the participant will not interact with the sensor in any other way. We will also provide instructions along with the shoes to remind participants how the sensor fits in the shoe and to troubleshoot any issues that may arise.

While the sensorized shoes have the storage capacity to record the amount of data that could be collected over the six weeks, there is the possibility of an incident leading to data loss. To mitigate potential data loss, the study trainer will schedule a meeting with the participant at a mutually agreed upon location during weeks 2 and 4. During this meeting the study trainer will download data from the sensor; no discussion of the intervention or the participants' progress will be discussed.

4.3.6 Control Condition: Wait period

Participants allocated to the Delayed Group at the baseline assessment will be sent home to

undergo a 6-week waiting period. During these 6 weeks they will be asked to maintain their current level of activity. No data will be collected during this time. After the 6-week waiting period, the Delayed Group will return for a secondary baseline (identical to the original baseline). This will constitute the pre-post data collection for the control condition. They will then enter the intervention condition as described above in section 4.3.5.

4.3.7 Data processing and analysis

Marker-based motion capture data (as collected during the baseline and follow-up assessments) will be processed using commercially available software using standard techniques our research group has used in previous studies [26, 30, 61, 62]. Sensorized shoe data captured during the baseline and follow-up gait assessment and at-home or community walking will be processed using custom MATLAB scripts.

4.4 Outcome Measures

4.4.1 Primary Outcome Measures

The primary outcomes of this study are those related to feasibility.

A) Modification Performance

- a. Change in FPA between baseline and the primary end point (6-week follow up). Measured via in-lab motion capture and the sensorized shoe during hallway walking.
- b. The change in FPA during at-home walking, comparing the mean baseline at-home walking FPA with each walking bout (represented by a single data file on the sensor module) recorded during the intervention period. Measures of FPA variability will be calculated (variance, standard deviation, interquartile range) in addition to the proportion of steps taken with $\geq 7^\circ$ of increase relative to their baseline FPA. Our previous results suggested 7° of change is required to elicit a statistically significant reduction in KAM magnitude [30, 31].

B) Adherence

- a. The total number of telerehabilitation sessions attended over the intervention period. Acceptable adherence is attending all 5 sessions.

C) Compliance

- a. Self-reported confidence in performing the gait modification during at-home walking. Measured via the weekly diary on an NRS scale (0 = no confidence at all, 10 = complete confidence). Acceptable confidence ratings by week 6 are $\geq 7/10$.
- b. Self-reported walking time using the sensorized shoe during at-home walking. Measured via the weekly diary. Acceptable walking time is an average of 70 minutes per week based on our instructions to walk a minimum of 10 minutes per day.

D) Difficulty

- a. Self-reported difficulty in performing the gait modification on an NRS scale (0 = no difficulty and 10 = most difficulty imaginable). Acceptable difficulty by week 6 is $\leq 4/10$.

E) Satisfaction

- a. Satisfaction with the gait modification program and the telerehabilitation sessions on a 7-point Likert scale where -3 = “extremely unsatisfied” and +3 = “extremely satisfied”. Scores of +2 or +3 will be considered “satisfied” and acceptable.

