Official Title: Foot progression angle modification: an exploratory six-week telerehabilitation intervention in people with knee osteoarthritis.

NCT Number: TBD

Document Date: February 3th, 2021

1 Objectives

The primary objective of this study is to examine the feasibility of conducting a gait modification intervention delivered using primarily a telerehabilitation model (video and/or teleconferencing). Specifically, we will assess 1) adherence and compliance to the program, 2) performance of the gait modification in laboratory and real-world settings, and 3) satisfaction with the program. We will also examine the effectiveness of the program by comparing 4) patient-reported outcome (e.g., pain and physical function) and 5) knee joint moments before and after the program.

2 Background

2.1 Knee OA is a costly public health problem impairing function and quality of life

Globally, knee OA is a leading cause of disability [1] and several epidemiological studies have suggested that knee OA affects approximately 12% of the adult population [2-4]. In Canada, OA accounts for annual direct and indirect costs in excess of \$27 Billion, stemming from health care services, treatments, and wage-related productivity losses [5]. Given the ageing population and concomitant increase in OA prevalence [6], the economic costs are also expected to rise. The large proportion of health care spending related to knee OA is allocated to surgical intervention (mainly knee replacement surgery), which only serves a small minority of patients with late-stage disease [7]. Therefore, inexpensive treatments to manage clinical and structural progression of majority of people with early- and mid-stage knee OA are needed.

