2.5 Monitoring performance and adherence

To date, most gait modifications for knee OA have focused on knee loading and clinical outcome measures, spending little time examining the actual performance of the modification itself (i.e. how accurately the individual executes the gait modification). When performance has been measured, it has typically been done in laboratory settings, before and after a modification intervention, and always in reference to a specific target [30, 31, 46]. It is likely these performances in laboratory settings are subject to the Hawthorne effect, and do not necessarily reflect performance outside the laboratory. Unfortunately, the performance of the modification during daily walking activities (outside the laboratory environment) is currently unknown, which constitutes an important gap in our knowledge. As performing the modification during daily walking is arguably more important than doing so in the laboratory setting it is vital that we quantify performance in these settings.

Given the potential of toe-in and toe-out walking modifications to benefit those with knee OA, it is important to address the limitations in our current knowledge before wider implementation can be expected. Our proposed study will be a pilot clinical trial focusing on self-directed FPA modification using a blended delivery (1 introductory session in person with the remainder via telecommunication). Performance and adherence to the gait modification will be monitored using a novel wearable sensor system co-designed by our research group and colleagues from Shanghai Jiao Tong University, Shanghai, China. This study will be the first knee-OA specific gait modification program delivered via telerehabilitation and will provide the first examination of performance and adherence to the program during daily walking activities.

3 Hypotheses

3.1 Primary hypothesis:

- H1: We expect participants will adhere to the program by attending an average of 70% of the scheduled video or telephone appointments. Participants will report increasing compliance with the program week over week.
- H2: Performance of the gait modification will improve over the six-week program. During real-world walking and the laboratory-measured gait assessment at follow-up, participants will exhibit increased FPA magnitude (more toe-in or toe-out) and decreased variability compared to baseline FPA.
- H3: Participants will report feeling satisfied with the gait modification program.

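### The satisfaction outcome puts the programme and the remote sessions on one scale with one cut-off; if asked as a single item, it cannot separate them

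*Protocol*

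**What the plan says.** Three places in the protocol bear on satisfaction.

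- **Objective and hypothesis.** Section 1 sets out to assess feasibility of a mainly remote intervention, including "3) satisfaction with the program". H3 in section 3.1 reads "Participants will report feeling satisfied with the gait modification program". Neither names the remote sessions as a separate object of satisfaction.
- **Questionnaire.** Item Q4 at follow-up (4.3.4 A) is "Satisfaction with the gait modification program and the telerehabilitation sessions using a 7-point Likert scale", running from -3 to +3. Item Q5 asks about the sessions alone: "Convenience of telerehabilitation sessions on an 11-point NRS". Item Q6 asks about the modification alone (difficulty in daily walking).
- **Outcome definition.** Section 4.4.1 E repeats the joint wording, "Satisfaction with the gait modification program and the telerehabilitation sessions on a 7-point Likert scale", and attaches one criterion: "Scores of +2 or +3 will be considered" satisfied and acceptable. The convenience item is not listed in 4.4.1 and has no acceptability threshold.

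SAP 1.1 says that feasibility outcomes will be reported by summary statistics, with the focus on the primary outcomes.

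**The concern.** The satisfaction line names two objects and gives them one scale and one cut-off. A participant who likes the coaching by video or telephone but dislikes walking with a changed foot angle, or the reverse, has no obvious single answer. Nothing in the protocol tells respondents how to combine the two.

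A feasibility trial exists to show what must change before a larger one. If satisfaction is low, the team needs to know whether to revise the remote delivery or the gait programme. If the two were rated together, summary statistics cannot recover the split afterwards, because the separate ratings were never collected.

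**Working it through.** The documents give no figure to reproduce here. The check is a comparison of the texts, followed by a small enumeration.

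**1. Is it one item or two?**

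| Place | Objects named | Scale | Cut-off |
|---|---|---|---|
| 4.3.4 A, follow-up item Q4 | programme and sessions | one, -3 to +3 | none given |
| 4.4.1 E | programme and sessions | one, -3 to +3 | one, +2 or +3 |
| 4.3.4 A, follow-up item Q5 | sessions (convenience) | 0 to 10 | none |
| 4.3.4 A, follow-up item Q6 | modification (difficulty) | 0 to 10 | none here; 4.4.1 D sets 4 or less by week 6 for difficulty |

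The natural reading is one rating, since there is one question number, one scale and one criterion. It is not the only reading. The same questionnaire lists "Perceived global rating of change in pain and physical function using a 15-point Likert" scale under one number, yet 4.4.2 F uses a global rating for knee pain alone. In that case joint wording stands for at least one separately usable score. Section 4.4.2 settles the matter for global change; nothing settles it for satisfaction.

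**2. What could a single score hide?**

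Suppose each respondent holds two private ratings, one for the programme and one for the sessions, each an integer from -3 to +3. There are 7 × 7 = 49 pairs. Two of the seven values (+2, +3) meet the cut-off and five do not.

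- Both components meet it: 2 × 2 = 4 pairs
- Exactly one meets it: 2 × (2 × 5) = 20 pairs
- Neither meets it: 5 × 5 = 25 pairs

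The protocol gives no answering rule, so three are assumed, with a combined score of at least +2 counted as satisfied:

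| Assumed rule | Pairs counted satisfied | Of these, one component below +2 | Pairs counted not satisfied | Of these, one component at +2 or more |
|---|---|---|---|---|
| Minimum of the two | 4 | 0 | 49 - 4 = 45 | 20 |
| Mean of the two | 6 | 2, namely (+1, +3) and (+3, +1) | 49 - 6 = 43 | 20 - 2 = 18 |
| Maximum of the two | 24 | 20 | 49 - 24 = 25 | 0 |

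These are counts of possible answers, not probabilities. Under the minimum rule a high score is clear and a low one is ambiguous. Under the maximum rule it is the other way round. Under the mean rule most of the ambiguity lies in the low scores. No rule makes both high and low scores clear.

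**3. What if there are already two ratings?**

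The ambiguity in the data disappears. Section 4.4.1 E would still not say which score the cut-off applies to, whether both must pass, or which one answers H3.

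**The case against.** The strongest reply has four parts.

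- **A single rating is not proven.** The form is not in the documents, and the global-change wording shows that this protocol can abbreviate. This stands, so the point is conditional and part of the fix may be only a clarification.
- **The programme includes its delivery.** Sections 1, 2.5 and 4.1 describe an intervention delivered mainly by telerehabilitation, so a combined rating is informative about the programme as delivered, which is what H3 and the objective concern. This also stands. A reader might infer that a joint score tells us nothing about H3 or about the acceptability of remote delivery. The documents do not support that: a high combined score is evidence for H3, and under the minimum rule it is unambiguous. The same reply means that a programme item will still partly reflect the sessions, so a split will not be perfectly clean. A session item beside it would nevertheless supply the rating that is otherwise missing.
- **Other measures help locate a problem.** On the delivery side there are attendance ("The total number of telerehabilitation sessions attended over the intervention period", with all 5 as the standard) and convenience. On the modification side there are confidence (at least 7/10 by week 6) and difficulty (at most 4/10). Trainers also review barriers at each session. This stands in part. These are indirect signs: a participant can attend all five sessions and be dissatisfied with them.
- **Little depends on it formally.** No test, target proportion or sample size is tied to satisfaction, which is one of five primary feasibility domains. This is true and limits the consequence, but the outcome is still primary and has a stated criterion.

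**Conclusion.** The point holds conditionally. As worded, satisfaction with the programme and with the remote sessions shares one 7-point scale and one cut-off. If it is administered as one item, the score describes the programme as delivered. The sessions cannot be separated out, and a low or mixed score cannot be attributed to either part.

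The size cannot be fixed from the documents. It depends on an unseen form and an unstated answering rule. For a high score, the ambiguity runs from none (0 of 4 pairs, minimum rule) to severe (20 of 24, maximum rule). For a low score it runs from 20 of 45 pairs (minimum rule) to none (maximum rule). If two ratings are already collected, what remains is a gap in the outcome definition. The matter affects how a primary feasibility result is interpreted, and no inferential analysis depends on it.

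**What to change.** Make item Q4 two explicit items on the existing -3 to +3 scale: (a) the gait modification programme, and (b) the telerehabilitation sessions. In 4.4.1 E, apply the existing +2/+3 cut-off to each and report each separately. Judge H3 on (a) and the acceptability of delivery on (b). List the convenience item (Q5) beside (b) in 4.4.1 E.

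The cost is one extra question at the follow-up visit and matching wording in 4.3.4 and 4.4.1. If the form already has two items, no new question is needed: say so in both sections, and state which item the cut-off and H3 refer to.
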